### **3.2.18      Extra-articular assessments**

The evolution of associated nonmusculoskeletal features including IBD, psoriasis and uveitis (including their severity), and flare rate history will be assessed as described in the protocol in the schedule of study assessments Table 5.1. For subjects experiencing a flare in Part B, corresponding assessments per visit are described in the protocol in the schedule of study assessments Table 5.2.

Incidence of uveitis flares, IBD exacerbations and psoriasis exacerbations will be provided from the extra-articular assessments.

### **3.2.19      Fecal and serum calprotectin**

The calgranulins, S100A8/S100A9 and S100A12, are calcium-binding proteins of the S100 family. They are released from activated monocytes and granulocytes at local sites of inflammation during the early phase of the immune response. Extracellularly, they exert important pro-inflammatory effects, thereby providing stimulation and amplification of the innate immune reaction. Calgranulins can be measured in serum and stool, and have been found to be very sensitive markers of innate immune activation. Moreover, the S100A8/S100A9 heterodimer, also called calprotectin, has been established for a long time as a fecal marker of disease activity in inflammatory bowel disease.

Fecal and serum calprotectin levels measured as numerical continuous variables will be assessed from the stool and serum samples collected during the study.

### **3.2.20      Inflammatory Bowel Disease Questionnaire (IBD-Q)**

The IBD-Q is a validated quality of life questionnaire, which combines an assessment of symptoms as a result of IBD, the way the subject has been feeling in general, and how their mood has been over the previous 2 weeks.

The IBD-Q contains 32 questions covering 4 domains of subjects' lives (bowel symptoms, systemic symptoms, emotional function, and social function).

Subjects will be asked to answer questions relating to the impact of their CD on their HRQoL over the 2 weeks prior to their study visit using the IBD-Q. The IBD-Q must be completed by the subject prior to start any study-related activities.

The method as detailed by Guyatt et al, 1989 will be used in the calculation of the IBD-Q score.

The total IBD-Q global score will be derived as the sum of the responses (from 1 to 7) to all 32 questions on the IBD-Q and can therefore range from 32 to 224. The IBD-Q score for each of the four categories (bowel symptoms, systemic symptoms, emotional function and social function) will be defined as the sum of the responses of the subset of questions of the IBD-Q as specified below:

- Bowel Symptoms Questions 1, 5, 9, 13, 17, 20, 22, 24, 26, 29
- Systemic Symptoms Questions 2, 6, 10, 14, 18
- Emotional Function Questions 3, 7, 11, 15, 19, 21, 23, 25, 27, 30, 31, 32
- Social Function Questions 4, 8, 12, 16, 28.

An IBD-Q response is defined as a clinically meaningful improvement in the total IBD-Q global score and corresponds to an increase in the total IBD-Q global score  $\geq 16$  points from Baseline. IBD-Q remission is defined as a total IBD-Q global score  $\geq 170$  points.

The following approach will be applied in the case of partially completed questionnaires.

The IBD-Q score for the four categories (bowel symptoms, systemic symptoms, emotional function and social function) will be calculated if only, at maximum, one of the items responses within the category is missing. The IBD-Q category score will be imputed by dividing the sum score with the number of available items responses and multiplying the result by the number of completed items within the category. If two or more items responses are missing within a category, the corresponding IBD-Q category score will be left missing.

The total IBD-Q global score will be calculated if four or less of the items responses are missing, as long as maximum one item per sub score is missing. The total IBD-Q global score will be imputed by dividing the sum score with the number of available items responses and multiplying the result by 32. If five or more items responses are missing, the corresponding total IBD-Q global score will be left missing.

#### Specific counting rules for answers provided to IBD-Q items

The following rules will apply for analysis of (1) out of range and (2) ambiguous answers (ie, invalid or unable to interpret answers) to questionnaires completed by subjects:

1. In case of out of range answer (ie, an answer that does not correspond to any possible response proposed in the questionnaire, e. g. "?", "I don't know" or any value superior or inferior to the ones specified in the response options): the answer will be scored as "missing". However, in case the subject selects one of the proposed responses but adds a comment (for example "6 +++" or "5 ?"), the response (ie, "6" or "5") will be retained for scoring but not the comment (ie, "+++" or "?"). In the same way, if the subject selects one of the proposed responses but adds a value superior or inferior to the ones specified in the responses options

(for example “4/5” or “-1/2” on a 5-point scale ranging from 0 to 4), the response corresponding to the possible responses options (ie, “4” or “2”) will be retained for scoring but not the values superior or inferior to the responses options (ie, “5” or “-1”).

2. In case of ambiguous answers (ie, multiple responses to a question allowing only a single response, a response marked between two allowed responses):

a. Multiple responses to a question allowing only a single response:

- If half or more responses are marked (ie, 4 responses marked on a seven point scale, 3 responses marked on a 5-point scale, 2 responses to a Yes/No item...): the answer will be scored “missing”.
- If less than half of the responses are marked:
- If the responses are NOT adjacent to each other: the answer will be scored “missing”,
- If the responses are adjacent to each other (“2/3” or “2/3/4”, for instance), the more severe score will be retained (ie the lowest item score for the IBD-Q).

b. If a response is marked between two allowed responses (for example, the subject marked his/her response between 2 and 3 on a 4-point scale allowing only responses 1, 2, 3 and 4): the nearest more severe (lowest) score will be retained.

### **3.2.21 Sustained Remission**

Sustained remission is achieved when a subject has an ASDAS <1.3 at Week 32 or Week 36 (if ASDAS <1.3 at Week 32, it must be <2.1 at Week 36; if ASDAS <2.1 at Week 32, it must be <1.3 at Week 36) and an ASDAS <1.3 at Week 48.

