#### **2.2.1.2 Secondary efficacy variables**

##### **2.2.1.2.1 Secondary efficacy variables for subjects entering Part A**

- Percentage of subjects achieving sustained remission at Week 48
- Ankylosing Spondylitis Disease Activity Score (ASDAS) disease activity (ASDAS-Inactive Disease [ASDAS-ID], ASDAS-Low Disease activity [ASDAS-LD] (formally called ASDAS Moderate Disease), ASDAS-High Disease activity [ASDAS-HD], and ASDAS-very High Disease activity [ASDAS-vHD]) and clinical improvement (ASDAS-Clinically Important Improvement [ASDAS-CII], ASDAS-Major Improvement [ASDAS-MI]) at Week 48

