### **2.4       Determination of sample size**

It is anticipated that approximately 210 subjects will be randomized in a 1:1:1 ratio to the CZP 200mg Q2W, CZP 200mg Q4W, and PBO treatment groups. The primary efficacy analysis is based on the proportion of subjects who do not experience a flare during Part B of the study. The proportion of subjects who do not experience a flare during Part B is assumed to be 80%, 75%, and 45% for the CZP 200mg Q2W, CZP 200mg Q4W, and PBO treatment groups, respectively. Given these assumptions, a sample size of 70 subjects per group provides 98% power to detect a significant difference between the CZP 200mg Q2W dose and PBO and 94% power to detect a significant difference between the CZP 200mg Q4W dose and PBO using a 2-sided significance level of 0.05.

Given that subjects enter Part B only if they have achieved sustained remission in Part A, it is necessary to estimate the number of subjects needed to enroll in Part A. It is assumed that approximately 28% of subjects enrolled in Part A will achieve sustained remission and qualify for Part B. This means that about 750 subjects will be enrolled in Part A in order to have 210 subjects who are randomized into Part B.

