- If more than one component is missing at a visit, the previous visit's total ASDAS score will be carried forward, assuming the previous visit was a post-baseline assessment. Otherwise the LOCF score is missing at that visit.

Disease activity is measured by binary response variables derived from ASDAS as follows:

- ASDAS-Inactive Disease (ASDAS-ID): ASDAS  $<1.3$
- ASDAS-Low Disease activity (ASDAS-LD): ASDAS  $\geq 1.3, < 2.1$
- ASDAS-High Disease activity (ASDAS-HD): ASDAS  $\geq 2.1, \leq 3.5$
- ASDAS-very High Disease activity (ASDAS-vHD): ASDAS  $> 3.5$

ASDAS improvement is measured by binary response variables defined as follows:

[figure not shown]
- ASDAS-CII: ASDAS reduction (improvement) of  $\geq 1.1$  relative to Baseline
- ASDAS-MI: ASDAS reduction (improvement) of  $\geq 2.0$  relative to Baseline. As a sensitivity analysis, ASDAS-MI analyses will be repeated using a Modified ASDAS-MI: ASDAS reduction (improvement) of  $\geq 2.0$  relative to Baseline or has the lowest score possible post-baseline (i.e. when CRP<LLOQ and all other components are 0, then the minimum ASDAS score is 0.636 to 3 decimal places).

[figure not shown]

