#### **8.2.1.1 Percentage of subjects achieving sustained remission at Week 48**

The number and percentage of subjects achieving sustained remission at Week 48 will be summarized in frequency tables by axSpA subpopulation and for all subjects combined. The 95% CI based on the Exact Binomial distribution will also be presented. The presentation will be done on the observed case data and will be repeated on the imputed data using NRI.

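### Read literally, the SAP's sustained remission rule (3.2.21) reduces to Week 36 and Week 48 ASDAS <1.3, so the Part A remission percentage can be miscounted in both directions

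*SAP*

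**What the plan says.** Section 3.2.21 is the only definition of sustained remission in the SAP. It has four parts:

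- Leading condition: "Sustained remission is achieved when a subject has an ASDAS <1.3 at Week 32 or Week 36".
- First bracketed condition: "if ASDAS <1.3 at Week 32, it must be <2.1 at Week 36".
- Second bracketed condition: "if ASDAS <2.1 at Week 32, it must be <1.3 at Week 36".
- Week 48 condition: "and an ASDAS <1.3 at Week 48".

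The definition feeds the first secondary variable listed for Part A in 2.2.1.2.1, "Percentage of subjects achieving sustained remission at Week 48". Section 8.2.1.1 says: "The number and percentage of subjects achieving sustained remission at Week 48 will be summarized in frequency tables by axSpA subpopulation and for all subjects". It adds an exact 95% CI, on observed cases and again with non-responder imputation (NRI). Section 2.3.2 makes the same criteria the condition for randomization into Part B. Section 2.4 plans on "approximately 28% of subjects enrolled in Part A will achieve sustained remission".

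**The concern.** The two bracketed conditions look like the two sides of the 'or': one of Weeks 32 and 36 is below 1.3 and the other is below 2.1. They are written instead as two 'if' statements that both apply, and their ranges overlap because every value <1.3 is also <2.1. Nor does either statement say what happens when Week 32 is 2.1 or higher.

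A programmer who follows the text exactly would reject some subjects whom the first condition is there to accept, and accept some whom the second is there to exclude. At stake is the numerator of a named secondary endpoint. Section 4.3 also says that the Week 48 interim analysis is meant to check the protocol's efficacy assumptions, and for the 28% assumption that check needs one unambiguous count. A literal derivation could also label some randomized subjects as not in sustained remission, so the disposition table (5.1) and the remission table (8.2.1.1) would not agree.

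**Working it through.** **The plan's own figure.** Section 2.4: 210 / 0.28 = 750 subjects enrolled in Part A. This reproduces.

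**Logic check.** Write W32, W36 and W48 for the ASDAS values and take W48 <1.3 throughout, since that part is the same under either reading.

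- As written: (W32 <1.3 or W36 <1.3), and (if W32 <1.3 then W36 <2.1), and (if W32 <2.1 then W36 <1.3).
- Apparent intent: (W32 <1.3 and W36 <2.1) or (W32 <2.1 and W36 <1.3).

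| W32 | W36 | Leading condition | First 'if' | Second 'if' | As written | Apparent intent |
|---|---|---|---|---|---|---|
| <1.3 | <1.3 | met | met | met | accept | accept |
| <1.3 | 1.3 to <2.1 | met | met | **fails** | **reject** | **accept** |
| <1.3 | >=2.1 | met | fails | fails | reject | reject |
| 1.3 to <2.1 | <1.3 | met | not triggered | met | accept | accept |
| 1.3 to <2.1 | 1.3 to <2.1 | not met | not triggered | fails | reject | reject |
| 1.3 to <2.1 | >=2.1 | not met | not triggered | fails | reject | reject |
| >=2.1 | <1.3 | met | **not triggered** | **not triggered** | **accept** | **reject** |
| >=2.1 | 1.3 to <2.1 | not met | not triggered | not triggered | reject | reject |
| >=2.1 | >=2.1 | not met | not triggered | not triggered | reject | reject |

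Two of the nine cells differ, one in each direction. The cells accepted as written are exactly the three with W36 <1.3. The rule has collapsed to W36 <1.3 and W48 <1.3: Week 32 no longer matters and the first 'if' never decides anything. Two example records (W32 / W36 / W48):

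- 1.0 / 1.8 / 1.1 fails as written but meets the apparent intent.
- 2.6 / 1.2 / 1.1 passes as written but does not meet the apparent intent.

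**Illustrative size.** The SAP gives no ASDAS distribution, so everything here is assumed. ASDAS at the three visits was taken as trivariate normal with a common mean, SD 0.8, 1.0 or 1.2, and equal between-visit correlation 0.6, 0.7, 0.8 or 0.9. The mean was solved so that the apparent intent gives 28%, or 210 of 750. There were 2,000,000 simulated subjects per setting.

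- Dropped by the literal rule: 21.4 to 40.9 of 750.
- Added by the literal rule: 0.1 to 12.8 of 750.
- Lowest literal count (SD 0.8, correlation 0.6): 174.4 of 750 = 23.3%. Shortfall (210 - 174.4) / 750 = 4.7 points.
- Highest literal count (SD 1.2, correlation 0.9): 189.4 of 750 = 25.3%. Shortfall (210 - 189.4) / 750 = 2.7 points.

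A second model gave a similar picture. It used a subject mean plus visit noise, floored at the 0.636 minimum in 3.2.7, with between-subject SD 0.8 and within-subject SD 0.3 / 0.4 / 0.5. It dropped 3.3 / 4.0 / 4.5 points and added 0.03 / 0.2 / 0.6, a net shortfall of about 3.3 / 3.8 / 3.9 points. Its last setting was calibrated only loosely: 23.7 + 4.5 - 0.6 = 27.6%, not 28%.

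**The case against.** The strongest reply is that nobody would program it that way. The two clauses follow an 'or' and are separated by a semicolon, so the natural reading is one clause for each side. The literal reading makes the first clause inert and removes Week 32 from a rule that names it repeatedly. Section 3.2.7 also treats inactive disease (<1.3) as a separate band from "ASDAS-Low Disease activity (ASDAS-LD): ASDAS" 1.3 to <2.1. A literal derivation would probably be noticed, because it would clash with the list of randomized subjects.

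Much of this stands. The intent is fairly evident, and the miscount arises only under literal programming. But a derivation rule should give one answer when two people program it independently. Nothing else in the SAP says that the clauses are alternatives or that the second starts at 1.3. The explicit lower bound in 3.2.7 shows that the document can state such a range when it needs to.

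The objection to the size also stands. The distributions are assumed and were calibrated to 28% under the apparent intent. The figures therefore measure the gap between two readings, not a departure from the plan, and 28% is only a planning assumption. Neither model includes dropout or missed visits.

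A reader might infer that the endpoint has been miscounted, that the wrong subjects entered Part B, or that the primary result is affected. The documents support none of these. They show no code and no count. Eligibility was applied in conduct under a protocol not shown here. The primary analysis (8.1.1) uses the Randomized Set, which is everyone randomized (3.6.3), so re-deriving remission does not change it. The Part A percentage is itself descriptive, with no hypothesis test.

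**Conclusion.** The point holds as a rule that is wrong as written. Applied literally, 3.2.21 becomes Week 36 <1.3 and Week 48 <1.3. The percentage in 8.2.1.1 can then be wrong in both directions and can disagree with who was randomized. The logic rests on the text alone. The apparent intent is inferred from the shape of the sentence and is not stated elsewhere in the SAP.

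The size cannot be derived from the documents. Under the assumed distributions, literal programming gives about 23% to 25% where the apparent intent gives 28%, roughly 3 to 5 points too low. Subjects wrongly dropped outnumber those wrongly admitted in every setting tried, so the two errors do not cancel. The consequence is confined to the Part A remission summary and its agreement with the randomized list.

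**What to change.** Reconcile 3.2.21 with the criterion actually applied for Part B entry. That is for the sponsor to confirm, and this review does not say which thresholds are clinically right. Then restate the definition as two explicit alternatives joined by 'or', each giving the threshold for both Week 32 and Week 36. The apparent intent would read:

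- (Week 32 <1.3 and Week 36 <2.1) or (Week 32 <2.1 and Week 36 <1.3); and
- Week 48 <1.3; and
- all three values non-missing, with subjects who have a missing value handled by NRI as in Section 4.2.

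Do not shorten this to a bare MIN/MAX expression. SAS, the software named in 3.1, ignores missing arguments in those functions. A subject with Week 32 = 1.0, Week 36 missing and Week 48 = 1.1 would then pass on a single early visit, contrary to NRI.

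The cost is a short rewording of one definition and a check of the program behind 8.2.1.1. No new data are needed.

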### **3.2.22 Flare**

A subject is considered to have experienced a flare if a subject has an ASDAS  $\geq 2.1$  at 2 consecutive visits or an ASDAS  $>3.5$  at any visit during Part B up until Week 96.

If a subject has an intermittent missing ASDAS score (ie, a missing value at 1 visit but non-missing values at the previous and subsequent visit), then the missing value will be ignored and the occurrence of a flare will be based on the 2 available values.

If the ASDAS score is missing at 2 or more consecutive visits, then the subject will be considered to have experienced a flare (even if ASDAS scores are available after the missed visits).

There is also the possibility to report one unscheduled ASDAS between two scheduled ASDAS assessments. The same rules as for the scheduled ASDAS apply for the unscheduled ASDAS.

The unscheduled ASDAS will be taken into account for flare calculation for two consecutive visits if there are more than 13 calendar days between two consecutive ASDAS calculated dates.

If the ASDAS score is missing at 2 scheduled visits and unscheduled ASDAS entry present in between and not larger than 3.5, then the subject will not be considered to have experienced a flare.

Occurrence of a flare will be based solely on the observed ASDAS values and will not take into account any imputation of ASDAS. Occurrence of a flare will be determined based on the actual

data entered into the eCRF for the individual ASDAS components, not based on data from the interactive voice or web response system (IXRS).

If a subject prematurely withdraws from Part B at any point for any reason, then the subject will be considered to have experienced a flare.

If a subject was incorrectly identified as flared at any point in Part B due to late data entry in IXRS and went to escape Part B, then the subject will be considered to have experienced a flare.

Sensitivity analyses will be conducted using different approaches for definition of flare. These approaches are described hereafter.

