### 3.2.23 Time to flare

The time to flare will be defined as follows:

- For subjects who meet the criteria for flare, the flare date will be defined as:
  - For subjects who first meet the criterion “ASDAS  $\geq 2.1$  at 2 consecutive visits”, the date of the second ASDAS score will be considered the flare date.
  - For subjects who first meet the criterion “ASDAS  $> 3.5$  at any visit”, the date of the corresponding ASDAS score will be considered the flare date.
  - The date of the ASDAS score is defined as the date the corresponding BASDAI/PtGADA assessments were performed and the CRP sample(s) was (were) collected. If the assessments were not performed on the same day, a conservative approach will be used, and the latest day will be taken as calculated ASDAS day.
- Subjects who discontinue the study without Withdrawal Visit will be treated as having experienced a flare at the next planned ASDAS visit. The final available ASDAS score date + 32 (4 Weeks + visit window) will be used as flare date. If Week 48 or Week 50 are last ASDAS visits, Week 48/Week 50 ASDAS date + 18. (2 weeks + visit window) will be used as flare date.
- Subjects who discontinue the study will be treated as having experienced a flare at the date of their withdrawal visit, if the last ASDAS visit date is not equal with the withdrawal date. If the withdrawal date is equal to the last ASDAS visit date, the same approach as for subject without Withdrawal Visit will be used for deriving the flare date.
- Subjects with missing ASDAS scores at 2 or more consecutive visits will be treated as having experienced a flare at the date of the second visit where the ASDAS score is missing, irrespective of whether the subject meets the flare criteria at a later time point.
  - If the date of the second missing ASDAS visit is available, the date of the visit will be used.
  - If the date of the second missing ASDAS visit is not available, the last ASDAS date + 60 (8 weeks + visit window) will be used as flare date. If Week 48 is the last ASDAS visits, Week 48 ASDAS date + 32. (4 weeks + visit window) will be used as flare date. If Week 50 is the last ASDAS visits, Week 50 ASDAS date + 46. (6 weeks + visit window) will be used as flare date.
- For subjects who complete the study without meeting the criteria for flare, the censored date will be the last possible date of the event, i.e. Week 96.

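### The unscheduled-ASDAS exception in SAP 3.2.22 can override the two-visit 2.1 flare criterion when both flanking scheduled scores are missing

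*SAP*

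**What the plan says.** SAP 3.2.22 defines a flare by two ASDAS criteria: at least 2.1 at two consecutive visits, or above 3.5 once. Around these it sets rules for missing and unscheduled scores:

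- A single missing score between two available ones: "then the missing value will be ignored and the occurrence of a flare will be based on the 2 available values".
- Two or more in a row: "If the ASDAS score is missing at 2 or more consecutive visits, then the subject will be considered to have experienced a flare".
- Unscheduled scores in general: "The same rules as for the scheduled ASDAS apply for the unscheduled ASDAS".
- Spacing needed from one ASDAS date to the next: "The unscheduled ASDAS will be taken into account for flare calculation for two consecutive visits if there are more than 13 calendar days".
- The exception, for a subject without a score at two scheduled visits but with an extra assessment separating them: "unscheduled ASDAS entry present in between and not larger than 3.5, then the subject will not be considered to have experienced a flare".

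Section 3.2.23 dates a flare under the 2.1 criterion by the second score: "the date of the second ASDAS score will be considered the flare date". For two consecutive missing scores, 3.2.23 and Table 3.3 give an event at the second missing visit in the main (NRI) approach. Neither mentions an unscheduled score in between.

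**The concern.** The exception follows the rule that two missing scores in a row are a flare, and it makes sense as a relaxation of that rule: a subject who was assessed between the two missed visits was not lost from view. Its consequence is wider than that purpose. It does not say that the missing-score rule is not met; it says that the subject has not flared. The only value it checks is 3.5, and it has no clause keeping the other flare criteria in force. The SAP does use such a clause elsewhere, in the alternative handling of premature withdrawal (3.2.22.2 and again in 3.2.23).

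This is the derivation of the primary variable. Two programmers working from the same text could classify the same subject differently, and a choice between the readings made after unblinding would be open to challenge.

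**Working it through.** **Rules applied to visit sequences.** Scheduled scores are taken 4 weeks apart, as in the date rules of 3.2.23. 'General rules' means the two ASDAS criteria, the single-missing rule and the same-rules sentence with its 13-day spacing. The exception column shows the literal result of the disputed sentence.

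| Sequence | General rules | Exception |
|---|---|---|
| 2.5; unscheduled 2.8 (14 days later); 1.5 | Flare | Not triggered |
| 1.5; unscheduled 2.8; 2.4 (14 days later) | Flare | Not triggered |
| 1.2; missing; unscheduled 2.8; missing; 1.4 | No flare | No flare |
| 1.2; missing; unscheduled 3.6; missing; 1.4 | Flare (above 3.5) | Not triggered |
| 2.5; missing; unscheduled 2.8; missing; 1.4 | Flare | **No flare** |
| 1.2; missing; unscheduled 2.8; missing; 2.5 | Flare | **No flare** |

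Only the last two rows conflict. Both need the two flanking scheduled scores to be missing, an unscheduled value from 2.1 to 3.5, and a nearest available score, before or after, that is also at least 2.1.

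**A dated example.** Week 60 = 2.6, Week 64 missing, unscheduled Week 66 = 2.9, Week 68 missing, later scores available and below 2.1.

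- Week 64 is a single missing score between two available ones, so it is ignored.
- The gap is 66 − 60 = 6 weeks = 42 days, more than 13.
- 2.6 and 2.9 are both at least 2.1, so the subject has flared.
- Weeks 64 and 68 are both missing and 2.9 is not above 3.5, so by the exception the subject has not flared.

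In time to flare, the general rules give an event at Week 66 and the exception gives censoring at Week 96. Section 3.2.23 and Table 3.3, read on their own with the two scheduled scores taken as consecutive, would give an event at Week 68. Section 4.2 says that the primary-endpoint rules carry over to time to flare, which argues against that last reading, but 3.2.23 does not say so itself.

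**Size.** The inputs are from SAP 2.4: 70 per arm and assumed flare-free rates of 80%, 75% and 45% for Q2W, Q4W and placebo.

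- The stated power reproduces. With a continuity correction, z = (|p1 − p2| − 1/n − 1.96·√(2·p̄(1 − p̄)/n)) / √((p1(1 − p1) + p2(1 − p2))/n).
  - Q2W: (0.35 − 0.0143 − 0.1604)/0.0763 = 2.30, power 98.9% (stated 98%).
  - Q4W: (0.30 − 0.0143 − 0.1623)/0.0788 = 1.57, power 94.1% (stated 94%).
- One reclassified subject moves an arm's rate by 1/70 = 1.4 percentage points; three (assumed) move it by 3/70 = 4.3 points.
- Direction depends on the arm. Suppose that two subjects per affected arm (assumed) move from flare-free to flare. Q4W power then goes from 94.1% to 93.7% if both arms are affected, 88.0% if only the CZP arm is, and 97.3% if only placebo is.

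**The case against.** The best reply is that the intent is plain. A lone score between two missing ones can by itself meet only the above-3.5 criterion, which explains why no other limit is named. Table 3.3 lists two consecutive scores of at least 2.1 as an event under all three approaches, and 8.1.3 counts ASDAS-defined flares found through unscheduled visits. Nothing suggests that the sponsor meant to cancel the 2.1 criterion. This stands as evidence of intent. It does not supply the missing order of precedence, and the sentence still says the opposite for the pattern above.

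Four stronger readings are tempting and are not supported:

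- *Any unscheduled ASDAS of 3.5 or less rules out a flare.* It does not: the exception requires missing scores at two scheduled visits with the unscheduled one in between. Otherwise the scheduled-visit rules apply, as the first two table rows show.
- *The conflict arises whenever the next scheduled score is at least 2.1.* If that score directly follows the unscheduled one, the flanking scores are not both missing and the exception is not triggered.
- *The false successes would fall mainly on placebo.* Unscheduled assessments may be more common after withdrawal, but the SAP gives no frequency by arm.
- *The observed-case analysis would call the same subject flared.* Section 3.2.22.1 restates neither the single-missing rule nor the unscheduled rules. If the general rules of 3.2.22 are imported to reach that result, the exception arguably comes with them.

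**Conclusion.** The point holds as a narrow defect in the primary-endpoint derivation. Followed literally, the exception scores as a success a subject whose two nearest available scores meet the 2.1 criterion, while other sentences of the same section score that subject as a flare. The size is 1.4 percentage points of an arm's rate per affected subject, on the planned 70 per arm. The number of affected subjects and the direction of any bias are unknown; the counts used above are assumptions for scale. The pattern needs several conditions together, so it may be rare. The sample-size calculation does not depend on it.

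**What to change.** Reword the exception in 3.2.22 to say: when the ASDAS is missing at two scheduled visits and an unscheduled ASDAS is available between them, the missing-ASDAS criterion is not met; the existing criteria (at least 2.1 at two consecutive available assessments more than 13 days apart, or above 3.5) continue to apply to the available values. Carry the same exception into the missing-ASDAS rule of 3.2.23 and the corresponding row of Table 3.3, so that event status and event date agree with 3.2.22.

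This sets no new threshold and concerns only the analysis derivation. It costs one sentence, two matching edits and a small change to the flare program, and should be made before unblinding.
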